12.1.3 Primary efficacy endpoints

Primary efficacy evaluation will be based on Full Analysis Set (FAS) and Per-Protocol Set (PPS). For the statistical description and inference of the data, the applicable descriptive endpoints and hypothesis testing methods will be selected based on the characteristics of the data.

The primary efficacy endpoint of this study is Lysholm score at 12 months after operation. The non-inferiority testing is performed for efficiency of primary efficacy endpoint, and the test hypothesis is as follows:

Invalid hypothesis: $H_0: \mu_1 - \mu_2 \leq -\delta$

Alternative hypothesis: $H_1: \mu_1 - \mu_2 > -\delta$,

where, μ_1 and μ_2 are the Lysholm scores in the investigational group and control group, respectively. δ is a non-inferiority critical value. At $\alpha=0.025$ (one-sided test), the hypothesis test is carried out using a two-sided t-test. A non-inferiority test is carried out on the Lysholm scores in the investigational group and control group. The 95% confidence interval between the two groups is calculated.

12.1.4 Secondary efficacy endpoints

The secondary efficacy evaluation is based on Full Analysis Set (FAS) and Per-Protocol Set (PPS).

Summary statistics of all other secondary variables will be given based on the nature of variables (continuous or classified variables). For continuous variables, the number of observations, mean, standard deviation, median, minimum and maximum will be reported. For classified variables, the number of observations, frequency and percentage will be reported.

12.2 Calculation of sample size

12.2.1 Total Sample Size

The primary efficacy endpoint of this study is the Lysholm score at 12 months after operation; the trial is designed as a non-inferiority trial. According to references, the non-inferiority margin is set as 5 in this study. Assuming that the variance in both the investigational group and control group is 9, the difference between two groups is 0, the significance level is set to $\alpha=0.025$ (one-tailed), power $1-\beta=0.80$, the calculation formula of sample size is analyzed by referring to the non-inferiority of quantitative indicator:

Confidential and Proprietary

This document contains confidential and proprietary information on Smith & Nephew PLC and Smith & Nephew, Inc. and is only available to Smith & Nephew and its manufacturers. Without prior written approval of Smith & Nephew, the content cannot be replicated, printed totally/partially or disclosed in any other way, and anyone must use it as per the requirements, either expressed or implied by Smith & Nephew.

Study Protocol - Device	Smith+Nephew
A Prospective, Multi-center, Randomized Clinical Study to Evaluate the Safety and Effectiveness of Biosure Regenesorb Interference Screw in Arthroscopic Reconstruction of Cruciate Ligaments in Chinese Patients	Study No.: BIOSURE RG.SMD.PMA.2019.01
	Version: V2.0/July 3rd, 2020
	Page 47 of 74

$$n_T = n_C = \frac{2(Z_{1-\alpha/2} + Z_{1-\beta})^2 \sigma^2}{(D - \Delta)^2}$$

In which, σ is the standard deviation; D is the mean difference between two groups, which is expected to be detected, $D=uT-uC$; Δ is the non-inferiority margin. At least 51 subjects should be included in each group in order to achieve 80% power, 102 in total. In consideration of 20% drop-out rate, 64 subjects are planned to be included in each group, 128 subjects in total; 12 subjects are planned to be added to increase the success rate of trial, 140 subjects in total and 70 in each group.

The estimation of sample size is completed by using PASS13.

12.2.2 Number of Subjects with Each Disease in Clinical Trial and Reason for Determination

In this trial protocol, it is strictly required that patients should be enrolled in compliance with the inclusion/exclusion criteria. It can be considered that all the patients have the same type of disease, and are not further divided.

12.2.3 In multi-center clinical trial, minimum and maximum number of subjects in each clinical trial institution and justification

This trial will be carried out at the same time in a number of clinical study sites. In principle, the number of subjects enrolled in each site will be distributed as evenly as possible to ensure adequate site representation. However, considering the feasibility and progress of the enrollment, the number of subjects enrolled will be adjusted according to the actual situation to ensure that the enrollment scale at each site is relatively balanced, and that the final enrollment scale for a specific site should not exceed 50% of the total number of cases.

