12.1 Statistical design, method and analysis procedure

12.1.1 Statistical analysis principles

The statistical software SAS 9.4 or above is used for statistical analysis. The sample size is calculated using PASS 13. Adopt the trial results for endpoint analysis. FAS and PPS are used to

Confidential and Proprietary

This document contains confidential and proprietary information on Smith & Nephew PLC and Smith & Nephew, Inc. and is only available to Smith & Nephew and its manufacturers. Without prior written approval of Smith & Nephew, the content cannot be replicated, printed totally/partially or disclosed in any other way, and anyone must use it as per the requirements, either expressed or implied by Smith & Nephew.

Study Protocol - Device	Smith+Nephew
A Prospective, Multi-center, Randomized Clinical Study to Evaluate the Safety and Effectiveness of Biosure Regenesorb Interference Screw in Arthroscopic Reconstruction of Cruciate Ligaments in Chinese Patients	Study No.: BIOSURE RG.SMD.PMA.2019.01
	Version: V2.0/July 3rd, 2020
	Page 45 of 74

analyze primary and secondary outcomes while SS is used to analyze safety indicators.

Unless otherwise specified, all significance tests and hypothesis tests use a two-sided test at a significance level of 5%. When appropriate, the obtained p value will be cited and the two-sided 95% confidence interval will be generated. All p values will be rounded to three decimal places. In all tables, the p values less than 0.001 will be expressed as "<0.001".

Continuous variables will be summarized using summary statistics such as mean, standard deviation, median, minimum, maximum, lower quartile (Q1) and upper quartile (Q3), etc. Classified and ordinal variables are summarized using frequency and percentage.

For comparison of general conditions in two groups, an appropriate method will be adopted based on the indicator type to carry out analysis. Continuous indicators in two groups will be evaluated using a two-sample t-test (if data is normally distributed) or the Wilcoxon rank-sum test (if data is non-normally distributed). Classified data will be analyzed using a chi-square test or the Fisher's Exact Test (if the chi-square test is not applicable), and ranked data using the Wilcoxon rank-sum test or CMH test.

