12.3 Significance level and power of the clinical trial

The statistical significance level takes the one-tailed significance level of $\alpha=0.025$, 80% power (1- β).

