12.5 Criteria for acceptability/unacceptability of clinical trial result

Primary efficacy endpoint (the Lysholm score at 12 months after operation): If the lower limit of 95% CI for the efficacy difference between two groups is greater than the non-inferiority margin, it is considered that the investigational product is non-inferior to the control product, the statistical hypothesis is valid and the result of clinical trial is qualified; otherwise, the hypothesis is invalid, and the result of clinical trial is unacceptable.

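### The sample size section assumes a variance of 9, which gives 6 per group; the stated 51 per group needs a standard deviation of 9 (variance 81)

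*Combined protocol and SAP*

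**What the plan says.** All the inputs are in section 12.2.1: a non-inferiority margin of 5 Lysholm points, an expected difference of 0, one-tailed alpha of 0.025 and 80% power. The variability assumption is worded "Assuming that the variance in both the investigational group and control group is 9". The formula printed below it has σ² in the numerator, and the key to the symbols reads "In which, σ is the standard deviation". The result is given as "At least 51 subjects should be included in each group in order to achieve 80% power, 102 in total". This is raised to 64 per group (128 in total) for 20% drop-out, and 12 more subjects bring the total to 140. On software the section says only "The estimation of sample size is completed by using PASS13"; it does not name the procedure or list the values entered. No standard deviation is given as a number in the section, and no other section gives one or restates the variance.

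**The concern.** The printed inputs do not lead to the printed answer. A variance of 9 is a standard deviation of 3, and on a score with a margin of 5 that calls for only a handful of patients per group. The stated result is roughly nine times larger, which is the ratio between a variance of 81 and a variance of 9.

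This is the only variability assumption behind the size of a registration trial. A regulator or ethics committee repeating the calculation would get 6 per group and could not reconcile it with 70. Later, anyone comparing the observed standard deviation with the plan would read a value near 9 as three times what was assumed, when it would in fact match the value apparently used.

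**Working it through.** **Inputs, all from section 12.2.1:** margin 5; true difference 0; one-sided alpha 0.025, so z = 1.9600; power 80%, so z = 0.8416. Allocation is 1:1 (section 10.1.3.3).

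**Formula.** With difference 0, the plan's formula becomes n per group = 2 × (1.9600 + 0.8416)² × σ² / 5². Here (2.8016)² = 7.849 and 2 × 7.849 / 25 = 0.6279, so n = 0.6279 × σ².

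**Reproducing the plan's 51, and testing the stated input:**

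| Assumption | σ² | n before rounding | n per group |
|---|---|---|---|
| Variance 9 (as written) | 9 | 5.65 | 6 |
| SD 8 | 64 | 40.19 | 41 |
| SD 9 | 81 | 50.86 | 51 |
| SD 10 | 100 | 62.79 | 63 |

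Of these whole-number standard deviations, only 9 returns 51.

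**Solving backwards.** σ = √(n × 25 / 2) / 2.8016. For n = 50 this is 8.924 and for n = 51 it is 9.012. The formula therefore rounds up to 51 only for a standard deviation above 8.924 and up to 9.012, a variance of about 79.6 to 81.2.

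**Can variance 9 be rescued by reading another input differently?** At 80% power, one-sided alpha of 0.05, 0.025 or 0.0125 gives 5, 6 or 7 per group by the normal formula, and 6, 7 or 9 by an exact t calculation. At 90% power the normal formula gives 7 to 9. To reach 51 with variance 9, the margin would have to be 3 × 2.8016 × √(2/51) = 1.66 rather than 5.

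**Later steps at SD 9.** 51 / 0.8 = 63.75, so 64 per group and 128 in total; 128 + 12 = 140, or 70 per group. Every later figure in the section is reproduced.

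**The Z subscript.** The formula prints Z with subscript 1−α/2 beside a one-tailed alpha of 0.025. Taken literally, that is Z(0.9875) = 2.2414, which at SD 9 gives 61.59, so 62 per group. The rest of the plan shows that 1.96 is meant:
- Section 12.1.1 sets two-sided testing at 5%.
- Section 12.1.3 pairs one-sided 0.025 with a two-sided procedure ("the hypothesis test is carried out using a two-sided t-test").
- Section 12.3 repeats the one-tailed 0.025.
- Section 12.5 judges the result on a 95% confidence interval.

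This is a notation slip only.

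**The case against.** The best defence is that this is one mislabelled word with no consequence. Section 12.6 rules out an interim analysis, no sample size re-estimation is described, and the decision rule in section 12.5 does not use the assumed variance. The chain to 140 is sound at SD 9, and a statistical reader would probably spot the slip. All of that stands, and it limits the importance of the point. It does not make the printed assumption correct.

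A second objection concerns the diagnosis. SD 9 is back-solved, and the result depends on the method. By an exact t calculation, SD 9 needs 52 per group, and 51 per group has power 0.793. An exact t calculation returns 51 only for standard deviations of roughly 8.84 to 8.92, which leaves out 9. Since the PASS procedure is not named, SD 9 cannot be proved from the document. It remains by far the likeliest reading, because the printed formula is the normal one and the printed number is 9. Variance 9 fails under either method: the exact t calculation gives 7 per group.

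The word is also not an artefact of reading the PDF. It stands in running prose, not in a table cell or an exponent.

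**Conclusion.** The point holds. As written, the variance assumption gives 6 per group, not 51. The stated figure requires a standard deviation of about 9 (variance about 81), with the margin, difference, alpha and power as printed and Z(0.975) in the normal formula. That the sponsor actually used SD 9 is an inference from the arithmetic.

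The change in enrolment is zero, and the trial's conclusion is not threatened. It should still be corrected, because the justification for the trial size cannot be reproduced from its own inputs.

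**What to change.** 1. Check the standard deviation, and the procedure, in the PASS 13 output.
2. If the value entered was 9, change the sentence in section 12.2.1 to a standard deviation of 9 in each group (variance 81). If it was something else, state that value and the procedure that gave 51.
3. In the same edit, either write the formula with Z(1−α) at one-sided alpha 0.025, or keep Z(1−α/2) and state two-sided alpha 0.05.

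If SD 9 is confirmed, the plan could also quote power for the t-test it intends to use; this is optional and corrects no error. Power at SD 9 is about 83% with 56 per group (70 × 0.8, assuming 20% have no usable primary value) and about 90% with all 70 per group analysed.

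The cost is one look at the software output and a wording correction. With SD 9 confirmed, enrolment stays at 140, and the margin, test and decision rule do not change.

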6.1 Trial objective

The objective of this study is to compare the safety and effectiveness of Biosure Regenesorb Interference Screw versus the control device in patients requiring repair or reconstruction of cruciate ligaments (including anterior cruciate ligament (ACL) and posterior cruciate ligament (PCL)). The trial results will be used for registration of Biosure Regenesorb Interference Screw in China.

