6.2 Study contents

This clinical trial is designed to be a prospective, multi-center, randomized, evaluator-blinded, parallel-controlled, non-inferiority trial. The primary efficacy endpoints are not inferior to the control group. The Biosure Regenesorb Interference Screw and BIOSURE HA Interference Screw are used in the trial and control groups, respectively, to evaluate the safety and effectiveness of the investigational medical device Biosure Regenesorb Interference Screw in clinical repair or reconstruction of knee cruciate ligament rupture or tear.

The subjects complying with the criteria for inclusion in this clinical trial will receive 24-month follow-up after being treated with the investigational product or the control product. The following endpoints will be recorded and evaluated: Lysholm score, IKDC score, Drawer test, Lachman test and imaging evaluation results at the follow-up visit at month 6, 12 and 24 after the operation, respectively, incidence and frequency of ADEs, AEs, and device deficiency throughout the trial and reoperation rate.

7 Background of Clinical Trial

The knee becomes one of the most injured joints due to its anatomical structure and particular function in human body. According to the statistics, there are 200,000 ACL rupture cases per year in the United States, including 100,000 requiring ACL reconstruction. An epidemiological investigation in sport injury showed that the total incidence of ACL injury is 0.47% in China. PCL injury are relatively infrequent. As reported in foreign literature, PCL injury has an incidence of 3% in the common population and account for 20% of knee ligament injury. No similar reports are found in China.

The ACL femoral attachment, located at the posterior part of the medial side of the lateral femoral

Confidential and Proprietary

This document contains confidential and proprietary information on Smith & Nephew PLC and Smith & Nephew, Inc. and is only available to Smith & Nephew and its manufacturers. Without prior written approval of Smith & Nephew, the content cannot be replicated, printed totally/partially or disclosed in any other way, and anyone must use it as per the requirements, either expressed or implied by Smith & Nephew.

Study Protocol - Device	Smith+Nephew

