10.1.3.3 Randomization/allocation

The randomization allows the patients to be given equal opportunity to be assigned to the trial group or control group, independently of investigators and/or subjective views of subjects, so that the various influencing factors tend to be distributed in a similar way, avoiding the issues of selection bias and information bias.

The subjects meeting all inclusion/exclusion criteria will be randomly allocated into any of two study groups (trial group or control group) in a ratio of 1:1 through network-based randomization system. The random number is allocated only when the subject has signed the Informed Consent Form and passes the screening test.

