10.1.4 Selection of subjects

10.1.4.1 Inclusion criteria

Subjects must meet all of the inclusion criteria:

Confidential and Proprietary

This document contains confidential and proprietary information on Smith & Nephew PLC and Smith & Nephew, Inc. and is only available to Smith & Nephew and its manufacturers. Without prior written approval of Smith & Nephew, the content cannot be replicated, printed totally/partially or disclosed in any other way, and anyone must use it as per the requirements, either expressed or implied by Smith & Nephew.

Study Protocol - Device	Smith+Nephew
A Prospective, Multi-center, Randomized Clinical Study to Evaluate the Safety and Effectiveness of Biosure Regenesorb Interference Screw in Arthroscopic Reconstruction of Cruciate Ligaments in Chinese Patients	Study No.: BIOSURE RG.SMD.PMA.2019.01
	Version: V2.0/July 3rd, 2020
	Page 27 of 74

- (1) Signing the Informed Consent Form (ICF) voluntarily;
- (2) Patients aged 18-75 years;
- (3) Patients clinically diagnosed with knee cruciate ligaments rupture or tear and suitable for cruciate ligaments reconstruction definitely;
- (4) Normal contralateral knee joint.

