10.1.5.2 Secondary efficacy endpoints

- Lysholm Score (Month 6, Month 24)
- International Knee Documentation Committee (IKDC) score (at months 6, 12 and 24)

The scoring scale was proposed in 2000 after being repeatedly revised by major sports medicine and medical organizations in Europe and America. The scale is composed of a knee evaluation form (10 items) and a knee ligament examination form (8 items), involving joint pain, sport level and ability of daily activities. The total score is 0-100. The IKDC scale is for evaluating the symptoms, functions and physical activities of the knee joint, helping compare different knee diseases.

- Drawer Test (Month 6, Month 12, Month 24)

Anterior drawer test: It is used for ACL examination. The patient should be supine with the knees flexed to 90 degrees and the feet flat on table and keep relaxed. The examiner sits on the examination table against the patient feet for fixation, grasps the tibia of the knee and draws the shank forward. The patient will be diagnosed with forward straight instability if the tibia is forward displaced 5 mm more than the uninjured side.

Posterior drawer test: It is used for PCL examination. The patient should be supine with the knees flexed to 90 degrees. The examiner places both hands behind the knee joint, with the thumbs on the extensor aspect. The proximal end of shank is repeatedly drawn backward. The posterior displacement of the tibia along the femur suggests partial or complete CL rupture.

Confidential and Proprietary

This document contains confidential and proprietary information on Smith & Nephew PLC and Smith & Nephew, Inc. and is only available to Smith & Nephew and its manufacturers. Without prior written approval of Smith & Nephew, the content cannot be replicated, printed totally/partially or disclosed in any other way, and anyone must use it as per the requirements, either expressed or implied by Smith & Nephew.

Study Protocol - Device	Smith+Nephew
A Prospective, Multi-center, Randomized Clinical Study to Evaluate the Safety and Effectiveness of Biosure Regenesorb Interference Screw in Arthroscopic Reconstruction of Cruciate Ligaments in Chinese Patients	Study No.: BIOSURE RG.SMD.PMA.2019.01
	Version: V2.0/July 3rd, 2020
	Page 32 of 74

- Lachman Test (Month 6, Month 12, Month 24)

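### ACL and PCL knees are pooled with no stated stratification, prespecified adjustment (for ligament or site) or result by ligament; the cost is precision and an adjustment left open until the data are seen

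*Combined protocol and SAP*

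**What the plan says.** - **Objective (6.1).** The trial concerns repair or reconstruction of the cruciate ligaments, "including anterior cruciate ligament (ACL) and posterior cruciate ligament (PCL". The indications in 9.1 list ACL repair and PCL repair as separate items.
- **Eligibility (10.1.4.1).** "Patients clinically diagnosed with knee cruciate ligaments rupture or tear and suitable for cruciate ligaments reconstruction definitely". There is no quota or cap for either ligament.
- **Pooling (12.2.2).** Under a heading on the number of subjects with each disease: "It can be considered that all the patients have the same type of disease, and are not further divided". The only ground given is that all patients meet the eligibility criteria, and those criteria admit both ligaments.
- **Allocation (10.1.3.3).** Subjects are allocated "in a ratio of 1:1 through network-based randomization system". No stratification factor or block is named.
- **Primary analysis (12.1.3).** "the hypothesis test is carried out using a two-sided t-test", with a 95% confidence interval. No covariate is named.
- **Secondary endpoints (10.1.5.2, 12.1.4).** "Anterior drawer test: It is used for ACL examination"; the posterior drawer test is for the PCL, and the Lachman test likewise has a forward and a reverse form. The analysis is summary statistics only, with no split by ligament.
- **Baseline (12.1.2).** Disease diagnosis is among the baseline variables. The groups are compared at baseline, and outcome data must be corrected before reporting if they are not balanced. No covariate, model or trigger is given, and ligament is not named.
- **Sites.** About four sites enrol competitively (10.1.4.6). Each has its own fixed rater (10.1.3.2, 13.2), and one site may supply up to half the cases (12.2.3).

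**The concern.** The plan separates the ligaments when it states its question and when it examines the knee, but not in the stated allocation or analysis. Two things are at stake.

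First, if ACL and PCL knees differ in 12-month Lysholm score, that variation stays in the error term of an unadjusted t-test. The same holds for site, which here also means rater, on a scale that 13.2 calls subjective. The remedy in 12.1.2 leaves open which variables to adjust for, how, and when. In a non-inferiority trial intended for registration, that choice should not follow sight of the data.

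Second, PCL is part of the stated question, but no PCL result is planned. One pooled Drawer or Lachman table would also mix different manoeuvres. The pre-operative and operative items listed in 10.2.2.2 and 10.2.2.3 do not explicitly name the torn ligament, so a later split may depend on how the diagnosis was recorded.

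**Working it through.** **Inputs from the plan:** margin 5; one-sided alpha 0.025; power 80%; spread 9; 51 per group, 64 after 20% dropout, raised to 70 (12.2.1).

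**Inputs that are assumptions:** the PCL share of trial patients (5% to 20%) and the ACL-PCL gap in mean Lysholm (5 to 10 points). The documents give neither. The nearest figure, in the background section, is that PCL injuries "account for 20% of knee ligament injury", which is a share of injuries and not of trial patients.

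**1. The plan's own figure.** n = 2 × (1.96 + 0.8416)² × 9² / 5² = 50.9, so 51 per group; 51 / 0.80 = 63.75, so 64. Both reproduce. The 9 must be a standard deviation: read as a variance, as 12.2.1 words it, the formula gives 6. SD 9 is used below as the total SD.

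**2. Pooled precision.** At 70 per arm, SE = 9 × √(2/70) = 1.52, and the 95% half-width is 1.96 × 1.52 = 2.98, about 3.0 points.

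**3. Size of a chance imbalance.** At a 20% share (28 of 140), the SD of the PCL count in one arm is √(28 × 0.25 × 112/139) = 2.37. The 95% range for the between-arm difference in PCL share is ±1.96 × 2 × 2.37/70 = ±13.3 percentage points. Multiplied by a gap of 5 or 10, this moves the mean difference by ±0.7 or ±1.3 points.

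**4. Where that shift sits.** It is a component of the 3.0-point half-width, not an addition to it. With PCL share p, the squared ratio of shift to half-width is p(1−p) × gap² / 81, which is the share of total variance due to ligament. For p = 0.20 and gap 10: 0.16 × 100/81 = 19.8%, and (1.33/2.98)² is about 20%.

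**5. What adjustment recovers.** SE reduction = 1 − √(1 − variance share). Power is from the noncentral t at 56 evaluable per arm (70 less 20%), against 83.0% unadjusted.

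| PCL share | Gap | Chance shift (95%) | Variance share | SE reduction | Half-width saved at 70 per arm | Power at 56 per arm |
|---|---|---|---|---|---|---|
| 10% | 5 | ±0.50 | 2.8% | 1.4% | 0.04 | 84.0% |
| 10% | 10 | ±0.99 | 11.1% | 5.7% | 0.17 | 87.1% |
| 20% | 5 | ±0.66 | 4.9% | 2.5% | 0.07 | 84.8% |
| 20% | 10 | ±1.33 | 19.8% | 10.4% | 0.31 | 90.2% |

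The documents give no basis for sizing the site effect, so none is claimed.

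**6. What a PCL-only result could show.** Half-width = t(0.975, 2n−2) × 9 × √(2/n), with n evaluable PCL knees per arm after 20% dropout.

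| PCL share | PCL knees of 140 | Evaluable per arm | Half-width | Power at margin 5 |
|---|---|---|---|---|
| 5% | 7 | 3 | 20.4 | 8% |
| 10% | 14 | 6 | 11.6 | 14% |
| 20% | 28 | 11 | 8.0 | 24% |

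A PCL-only test at 80% power would itself need 51 per arm, or 64 with dropout.

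**The case against.** Pooling is a defensible design. Sections 8.3 and 10.2.2.4 describe one population and one fixation technique, 10.1.5.1 supports the Lysholm score for cruciate reconstruction generally, and no separate PCL hypothesis is stated. Section 12.2.2 is a sample-size statement that says nothing about allocation or covariates. Section 10.1.3.3 is silent on strata, which is not the same as specifying simple randomisation. Section 12.7 refers to a statistical analysis plan that could hold more detail.

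A reader might infer that chance imbalance goes uncontrolled. The documents do not support that: 12.1.2 requires a baseline comparison and a correction, and disease diagnosis is among the baseline variables. A reader might also take the 0.7 to 1.3 point shift as a bias on top of the reported interval. It is not; step 4 places it inside the interval, and it rests on assumed inputs, with 1.3 needing both upper values together.

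All of this stands. It does not supply what is missing: a named covariate, a model, a trigger, or any result by ligament. A later choice of adjustment is also weaker evidence than one fixed in advance.

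The objection that a by-ligament table cannot show non-inferiority in PCL knees is correct as well. It is a reason to call the table descriptive and to state the limit, not to omit it.

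**Conclusion.** The point holds as a matter of precision and prespecification, not of validity. Under unstratified 1:1 allocation the t-test keeps its type I error, because its standard error includes ligament imbalance. If PCL knees score an assumed 5 to 10 points lower, leaving ligament out forgoes a standard-error reduction of 1.4% to 5.7% at an assumed 10% share and 2.5% to 10% at 20%. That is 0.04 to 0.31 points of a half-width of about 3.0. The open correction in 12.1.2 matters at least as much: its effect cannot be bounded from the documents, because neither its form nor its trigger is stated.

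A reader might infer that a positive pooled result would show non-inferiority for PCL, or that a table by ligament would settle it. Neither follows. At an assumed 5% to 20% share, a PCL estimate has a half-width of about 8 to 20 points against a margin of 5, and about 8% to 24% power.

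**What to change.** - **12.1.3:** replace the unadjusted t-test with a prespecified linear model for 12-month Lysholm with treatment, ligament (ACL/PCL) and site, and use its 95% confidence interval for the non-inferiority decision.
- **12.1.2:** let this model replace the open-ended correction. Keep the baseline comparison as description only.
- **10.1.3.3:** if randomisation has not begun, stratify the web system by one factor, for example site, and adjust for the other. Crossing two ligaments with about four sites gives eight strata; at a 10% share, 14 PCL knees over four sites is 3 to 4 per cell.
- **Data collection:** record the torn ligament explicitly, with a rule for knees in which both are reconstructed.
- **Reporting:** give the Lysholm difference with its 95% interval, and Drawer and Lachman results, descriptively by ligament.
- **12.2.2:** state that the trial is sized for the pooled population and not powered for a separate PCL conclusion.

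The cost is a few degrees of freedom, one extra table and one factor in the existing web system. No larger sample is needed unless a formal PCL claim is sought. If randomisation has already started, everything except the stratification can still be done, provided the model is fixed before the outcome data are examined.
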